## LIST OF ABBREVIATIONS AND DEFINITIONS OF TERMS

AE	adverse event
ALT	alanine aminotransferase
AST	aspartate aminotransferase
AUC	area under the curve
BUN	blood urea nitrogen
CFR	Code of Federal Regulations
CGM	Continuous glucose monitoring
CRO	contract research organization
CRU	clinical research unit
CTCAE	Common Terminology Criteria for Adverse Events
DBP	diastolic blood pressure
ECG	electrocardiogram
eCRF	electronic case report form
EDC	electronic data capture
EDTA	ethylenediaminetetraacetic acid
EW	early withdrawal
FDA	Food and Drug Administration
FPG	fasting plasma glucose
FSH	follicle-stimulating hormone
GCP	Good Clinical Practice
GGT	gamma-glutamyltransferase
GI	gastrointestinal
GLP-1	glucagon-like peptide 1
HbA1c	hemoglobin A1c
HBV	hepatitis B virus
HCV	hepatitis C virus
HIPAA	Health Insurance Portability and Accountability Act of 1996
HIV	Human Immunodeficiency Virus
HR	heart rate
IB	Investigator's Brochure

---

ICF	informed consent form
ICH	International Council for Harmonization
IND	Investigational New Drug application
IRB	Institutional Review Board
IUD	intrauterine device
MedDRA	Medical Dictionary for Regulatory Activities
PD	Pharmacodynamic
PI	Principal Investigator
PK	Pharmacokinetic
SAE	serious adverse event
SBP	systolic blood pressure
SBTI	soybean trypsin inhibitor
SOP	standard operating procedure
T1D	Type 1 diabetes
TEAE	treatment-emergent adverse event
TSH	thyroid stimulating hormone
ULN	upper limit of normal
WCBP	woman of childbearing potential
WHO	World Health Organization

## 1 INTRODUCTION

Diabetes mellitus is a chronic metabolic disorder that has reached epidemic proportions in the United States, affecting almost 8% of the U.S. population in 2007 (Centers for Disease Control and Prevention, 2008). Diabetes mellitus is defined by hyperglycemia (increased concentration of glucose in the blood) caused by defective insulin secretion (Type 1, T1D), resistance to insulin action (Type 2, T2DM), or a combination of both. Diabetes mellitus leads to an increased risk of microvascular damage (retinopathy, nephropathy and neuropathy), reduced life expectancy, increased risk of macrovascular complications (ischemic heart disease, stroke, and peripheral vascular disease), and diminished quality of life. This illness requires continuing medical care, subject self-management, and education to prevent acute complications and reduce the risk of long-term complications (American Diabetes Association, 2009).

The treatment goal for subjects with this disease is long-term glycemic control (over both fasting and non-fasting blood glucose levels), which has been demonstrated in both T1D and T2DM subjects to reduce the morbidities associated with uncontrolled glycemic levels (Diabetes Control and Complications Trial Research Group, 1993; Cleary et al., 2006; UK Prospective Diabetes Study Group, 1998a & 1998b). Typical options for glycemic control in subjects with T1D include two or more injections of insulin daily, with doses adjusted on the basis of self-monitoring of blood glucose levels. Insulin replacement is accomplished by giving a basal insulin and pre-prandial insulin. The basal insulin is either long acting (glargine or detemir) or intermediate-acting (NPH). The pre-prandial insulin is either rapid-acting (lispro, aspart, or glulisine) or short-acting (regular).

Glycemic control is measured by subject self-monitoring of blood glucose (SMBG), subject self-monitoring of interstitial glucose, and periodic blood tests for measurement of hemoglobin A1C (HbA1c or A1C). HbA1c levels reflect average glycemia over several months and therefore provide a surrogate for glycemic control (U.S. Food and Drug Administration, 2008). A consensus statement written by the American Diabetes Association and the European Association for the Study of Diabetes targets an HbA1c level of <7% as an objective for nonpregnant adults, who do not have complicating factors, for the prevention of micro- and macrovascular disease (Nathan et al., 2009).

Subcutaneously administered insulin is highly effective at lowering glycemia and helping subjects achieve target HbA1c levels. Insulin has no overall dose limit with respect to safety (except for hypoglycemia) and provides an improved lipid profile. However, subcutaneously administered insulin requires daily injections and blood glucose monitoring, and is associated with weight gain and an increased risk of hypoglycemia. Insulin is available as formulations with different pharmacokinetic (PK) and pharmacodynamic (PD) profiles (e.g, rapid, regular,

intermediate, or long acting, or mixtures of these). These different formulations are used to tailor appropriate insulin regimens on a per subject basis (Nathan et al., 2006).

ORMD-0801 is based on Oramed's platform technology for the oral delivery of polypeptides, which includes a proprietary formulation of excipients to facilitate oral uptake by hindering proteolysis in the small intestine and facilitating translocation of peptides across the gut epithelial lining, and into the systemic circulation. The formulation for ORMD-0801 includes soybean trypsin inhibitor (SBTI) to hinder proteolysis, and disodium ethylenediaminetetraacetic acid (EDTA) to facilitate translocation. The fish oil provides omega-3 fatty acids. The enteric-coated capsules are designed to disintegrate in a pH- dependent manner in the small intestine. The initial indication for ORMD-0801 is to reduce fasting blood glucose in adult subjects with Type 2 diabetes mellitus with the objective of controlling the overall average glycemic level.

The potential advantage of oral insulin in the treatment of elevated fasting blood glucose as compared to subcutaneously-administered insulin lies in the more physiological mechanism of delivery. Orally-administered insulin, once transported across the gut wall, is ferried to the hepatic portal vein, mimicking the natural route of endogenous pancreatic insulin and delivering the insulin directly to the intended site of action. In contrast, subcutaneously-administered insulin reaches the liver through the systemic circulation thereby requiring higher systemic levels of insulin in order to achieve the same effect. Thus, oral insulin administration (in combination with subcutaneously administered insulin) is expected to provide more physiological and improved control of blood glucose in Type 1 diabetes patients. This will reduce their risk of hypoglycemia and may prevent weight gain. The PK/PD profile of ORMD-0801 is well-suited to the control of fasting blood glucose due to the delayed onset.

Oramed has completed five Phase 1 safety studies of various formulations of ORMD-0801 in healthy human volunteers. Four Phase 2 studies have been completed, two in patients with T2DM, and two in patients with T1D. These Phase 2 studies investigated different formulations, the effect of meals at different times following ORMD-0801 administration, and the effect of ORMD-0801 on glucose as measured by continuous glucose monitoring (CGM) over a ten-day treatment period with three doses per day prior to meals. Notably, one Phase 2 study assessed the safety and effectiveness on fasting blood glucose of repeat bed time administration of ORMD-0801 in patients with T2DM over a period of 6 weeks. A Phase 1/2 dose-response study was also conducted. These studies demonstrated that the drug product is well-tolerated and can effectively reduce plasma glucose and C-peptide levels. There were no significant safety observations and no serious adverse reactions were reported for the completed studies, although there were two self-reported events of hypoglycemia in the six-week, Phase 2 study.

Oramed intends to continue the clinical development of ORMD-0801.

## 2 STUDY OBJECTIVES AND ENDPOINTS

### 2.1 Objectives

#### 2.1.1 Primary Objective

1. To compare the impact of Oral Insulin dosed QD to Oral Insulin dosed TID on exogenous basal and bolus insulin requirements in subjects with Type 1 Diabetes (T1D) during the last 10 days of each treatment period.
2. To compare the impact of Oral Insulin dosed QD to Oral Insulin dosed TID and associated adjustments of basal and bolus insulin on mean 24-hour glucose and parameters of glycemic variability as measured by a Continuous Glucose Monitor over the last 10 days of each treatment period.

#### 2.1.2 Secondary Objectives

1. To compare the change from baseline in number of hypoglycemic episodes in subjects treated with Oral Insulin dosed QD to Oral insulin Dosed TID in subjects with T1D over the last 10 days of each treatment period
2. To compare the change from baseline in HbA1C levels in subjects with T1D treated with Oral Insulin dosed QD or Oral Insulin dosed TID as measured at the end of each treatment period.
3. To explore differences in glucodynamics between the different dosing regimens during the last 10 days of each treatment period.
4. To evaluate the safety of Oral Insulin through the recording of adverse events, clinical laboratory test results (hematology, chemistry and urinalysis) and vital signs.

### 2.2 Endpoints

#### Primary Endpoints

1. To compare the amount of basal, bolus and total (basal + bolus) exogenous insulin utilized over the final 10 days of each treatment period.
2. To compare the impact of Oral Insulin dosed QD to Oral Insulin dosed TID and associated adjustments of basal and bolus insulin on mean 24-hour CGM glucose levels during the final 10 days of each treatment period.

#### Secondary Endpoints

3. Glucodynamics over the final 10 days of each treatment period as measured by CGM:
  - a. Time in range 70 - 180 mg/dL
  - b. Time <70 mg/dL
  - c. Time >180 mg/dL
  - d. Time >250 mg/dL
  - e. Glucose Coefficient of Variation
  - f. Low Blood Glucose Index (LBGI)

- g. Glucose below 70 mg/dL Area Over the Curve (AOC70)
4. Total daily non-oral insulin requirements in units per kilogram (kg) body weight over the last 10 days of each treatment period.

Exploratory Endpoints:

5. HbA1c measured at the end of each treatment period
6. Patient dairy-reported carbohydrate intake over the final 10 days of each treatment period
7. Changes in body weight from baseline (Visit 2) to the end of each treatment period
8. Other measures of hypoglycemia:
  - a. Severe hypoglycemia (SH) events (impaired or loss of consciousness requiring assistance of another)
  - b. Documented symptomatic hypoglycemia (an event during which typical symptoms of hypoglycemia are accompanied by a measured plasma glucose concentration <70 mg/dL (3.9 mmol/L))
  - c. Total time <70 mg/dL by CGM
  - d. Nocturnal hypoglycemia, severe or documented symptomatic episodes (as defined above) occurring after the subject has retired for the primary sleeping period

Safety assessments evaluating:

- Changes in clinical laboratory tests (hematology, chemistry, urinalysis);
- Collection of adverse events (AEs);
- Changes in Vital signs measurements

## 3 INVESTIGATIONAL PLAN

### 3.1 Overall Study Design and Plan

This study is designed to compare ORMD-0801 given QD versus TID in subjects with T1D. The study will consist of seven visits (including Screening Visit).

During Screening, subjects will be required to sign the informed consent form. Medical and medication history and demographic information will be collected. Eligibility for participation will be evaluated. Vital signs (height, weight, seated SBP/DBP, and heart rate) will be measured, physical examination will be performed, and a blood and urine sample will be collected for hematology/chemistry/urinalysis.

Eligible subjects will be scheduled to return to the clinic in 1 week (Visit 2). Subjects fulfilling all inclusion/exclusion criteria will have a CGM placed, provided with a diary, dispensed placebo capsules and asked to return to the clinic in 10 days (Visit 3, Day 1) for randomization. At Visit 3, data from CGM will be downloaded and diaries will be collected. Blood samples

will be collected in fasting for chemistry and HbA1C. Subjects will be randomized to receive either ORMD-0801 24 mg given once daily at bedtime, or ORMD-0801 8 mg given three times a day, 45-90 minutes before meals. Subjects will be instructed to continue their normal diet, and to adjust their basal and bolus insulin in the normal fashion. Subjects will be instructed to return to the clinic in 10 days before Visit 5 (Visit 4, Day 18). At Visit 4, compliance will be assessed, IMP and diary dispensed and the CGM will be placed. Subjects will be instructed to return to the clinic in 10 days for Visit 5 (Day 28). At Visit 5 a blood sample for chemistry panel and HbA1C will be drawn, the diary collected, the CGM removed and the patient will be crossed over to the alternate treatment regimen. IMP will be dispensed, and the subject will be asked to return in 10 days before Visit 7 for Visit 6 (Day 46). At Visit 6, compliance will be checked, IMP and a diary will be dispensed and the CGM will be placed. Subjects will be instructed to return in 10 days for Visit 7 (Day 56). At Visit 7 the CGM will be removed, the diary will be collected, compliance checked, blood sample will be drawn for a chemistry panel and HbA1C. A physical examination will be performed, and the subject will exit the study.

Subjects will be provided with diaries at Visits 2, 4 and 6, and will be asked to capture the amount of basal and bolus exogenous insulin administered each day and calculate their carbohydrate count for all meals and snacks over the 10-day CGM monitoring period of each treatment period.

### **3.2 Screening (-21 Days prior to Randomization)**

At the Screening Visit, potential subjects will be given a detailed oral presentation describing the nature, purpose, risks, and requirements of the study and will receive detailed written information. Subjects will be given ample time to consider participation and ask questions which will be adequately addressed by site personnel.

Once the subject is satisfied that he/she is willing to participate in the study, he/she will be asked to sign the study ICF (refer to Section 11.2.4 for further details regarding the ICF). The investigational site personnel obtaining written consent from the subject will also sign the consent form.

Once signed, the Investigator will retain the original ICF for the subject's study records and provide the subject with a signed copy. The investigator will verify that informed consent has been obtained from each subject prior to enrollment into the study and prior to the subject undergoing any study-related procedures.

Screening activities after obtaining informed consent will be conducted and consist of the following:

- Completion of medical history (including start date for T1DM),
- Collection of demographic data (sex, age, race/ethnicity);

- Review of prior and current medications and supplements;
- Review inclusion and exclusion criteria.
- Physical examination.
- Measurement of height and weight.
- Measurement of vital signs (SBP/DBP and heart rate).
- 12-lead electrocardiogram (ECG).
- Collection of fasted blood and urine samples for:
  - Clinical safety labs, including hematology, serum chemistry (with fasting plasma glucose/FPG, HbA1c, C-peptide, and serum thyrotropin/TSH, FSH to confirm postmenopausal status in women, and urinalysis (see Section 6.3.5 for list of tests);
  - Infectious serology (HIV, HBV, HCV);
  - Serum pregnancy Test for women of childbearing potential

For subjects who meet eligibility criteria based on the Screening assessments, instruction will be provided on the following:

- Use of adequate contraceptive methods (see Section 4.1) for the duration of the study (Screening through Visit 7);
- Minimal use of concomitant medications during the study, if possible, and avoid prohibited medications as defined in Section 5.7;
- Maintenance of usual dietary habits and avoidance of drastic changes, such as a conversion to a vegetarian diet;
- Restraint from excessive caffeine use (i.e., more than five cups of caffeinated beverages per day) during the study.

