	
b. has had a hysterectomy and/or bilateral oophorectomy, or had bilateral tubal ligation or occlusion at least 6 weeks prior to Screening
 
6. Subjects who are of childbearing potential must:
 
a. agree to remain abstinent from heterosexual activity† or agree to use (or have their partner use) acceptable contraception to prevent pregnancy within the projected duration of the trial and for 14 days after the last dose of blinded investigational product. Two methods of contraception will be used to avoid pregnancy. Acceptable combinations of methods include:
 

i. Use of one of the following double-barrier methods: diaphragm with spermicide and a condom; cervical cap and a condom; or a contraceptive sponge and condom

ii. Use of hormonal contraception (any registered and marketed contraceptive agent that contains an estrogen and/or a progestational agent [including oral, subcutaneous, intrauterine and intramuscular agents, and cutaneous patch]) with one of the following: diaphragm with spermicide; cervical cap; contraceptive sponge; condom; vasectomy; or IUD.

iii. Use of an IUD with one of the following: condom; diaphragm with spermicide; contraceptive sponge; vasectomy; or hormonal contraception (see above).

iv. Vasectomy with one of the following: diaphragm with spermicide; cervical cap; contraceptive sponge; condom; IUD; or hormonal contraception (see above).

 
†Abstinence can be used as the sole method of contraception if it is in line with the subject's preferred and usual lifestyle and if considered acceptable by local regulatory agencies and ethics committees. Periodic abstinence (e.g., calendar, ovulation, sympto-thermal, post-ovulation methods, etc.) and withdrawal are not acceptable methods of contraception.

	
Exclusion Criteria

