### **3.4 Visit 3 (Day 1 ± 2 days)**

Subjects will report to the CRU in the morning in fasting state. The following procedures will be performed:

- Collect data from CGM monitor;
- Review of medications and supplements;
- Collect and review diary;
- Measurement of vital signs (weight, seated SBP/DBP, and heart rate);
- Urine pregnancy Test for women of childbearing potential
- Collect fasting blood samples for serum chemistry (with fasting plasma glucose/FPG) and HbA1c;
- Review inclusion and exclusion criteria.
- Randomization of subjects to their individual study treatment sequence;
- Dispensing of IMP and instructions on use of IMP.
- Adverse events will be monitored and recorded.

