### 3.8 Visit 7 (Day 56 ± 2 days)

Subjects will report to the CRU in the morning in fasting condition. The following procedures will be performed:

- Review of medications and supplements;
- Collect data from CGM monitor;
- Collect and review diary;
- Measurement of vital signs (weight, seated SBP/DBP, and heart rate);
- Physical examination;
- Collect fasting blood samples for hematology, serum chemistry (with fasting plasma glucose/FPG), HbA1c and urinalysis;
- Returning of IMP;
- Assessment of compliance to IMP;
- Adverse events will be monitored and recorded.
- Discharge from the study.

Any subject with a possible study treatment related AE at Visit 7 will be followed until resolution or stabilization of the event. Further, any SAE, whether or not related to study treatment that occurs within 14 days following the last dose of study treatment will be followed until resolution or stabilization of the event. This may require additional clinical assessments and laboratory tests. The follow-up results will be recorded in the subject's source documentation and in the electronic case report form (eCRF).

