**Table 1. Daily Schedule of Events from Screening Through Visit 7**

Visit	Screening Visit 1	Visit 2	Randomization Visit 3	Visit 4	Visit 5	Visit 6	Visit 7	EW
Study Day	-21	-10	1	18	28	46	56	
Window days	$\pm 2$	$\pm 2$	$\pm 2$	$\pm 2$	$\pm 2$	$\pm 2$	$\pm 2$	
Informed Consent	X							
Medical History	X	X						
Demographics	X							
Concomitant Medications	X	X	X	X	X	X	X	X
Inclusion/Exclusion Criteria	X	X	X					
Physical Exam	X						X	X
ECG	X							
Vital Signs	X	X	X	X	X	X	X	X
Serum Pregnancy Test	X							
Urine Pregnancy Test			X		X			
Infectious Serology (HIV, HBV, HCV)	X							
C-peptide, TSH, FSH	X							
Hematology	X						X	X
Serum Chemistry (with FPG)	X		X		X		X	X
HbA1c	X		X		X		X	X
Urinalysis	X						X	X
Randomization			X					
Treatment Crossover					X			
Treatment Compliance			X	X	X	X	X	X
Treatment dispensing/returning		X	X	X	X	X	X	X
CGM Monitoring		X	X	X	X	X	X	X
Diary dispensing/collecting		X	X	X	X	X	X	X
Adverse Events			X	X	X	X	X	X
Study Disposition							X	X

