## 4 STUDY SUBJECT SELECTION

### 4.1 Inclusion Criteria

Each subject must meet all of the following criteria to be eligible for study participation:

1. Male and female (non-childbearing potential) subjects aged 18 and older.
2. Body mass index (BMI) of 19-30 kg/m^2 at Screening and stable weight, with no more than 5 kg gain or loss in the 3 months prior to Screening.
3. T1D subjects must have:
  - a. A documented history of type 1 diabetes for at least 6 months
  - b. Should be on an MDI regimen
  - c. C peptide levels of < 0.7 ng/mL
  - d. HbA1C  $\geq$  6.5% to  $\leq$  10%
4. Females of childbearing potential must have a negative serum pregnancy test result at Screening.
5. Females who are not of childbearing potential are defined as:
  - a. post-menopausal (defined as at least 12 months with no menses in women  $\geq$  45 years of age) or
  - b. has had a hysterectomy and/or bilateral oophorectomy, or had bilateral tubal ligation or occlusion at least 6 weeks prior to Screening
6. Subjects who are of childbearing potential must:
  - a. agree to remain abstinent from heterosexual activity† or agree to use (or have their partner use) acceptable contraception to prevent pregnancy within the projected duration of the trial and for 14 days after the last dose of blinded investigational product. Two methods of contraception will be used to avoid pregnancy. Acceptable combinations of methods include:
    - i. Use of one of the following double-barrier methods: diaphragm with spermicide and a condom; cervical cap and a condom; or a contraceptive sponge and condom
    - ii. Use of hormonal contraception (any registered and marketed contraceptive agent that contains an estrogen and/or a progestational agent [including oral, subcutaneous, intrauterine and intramuscular agents, and cutaneous patch]) with one of the following: diaphragm with spermicide; cervical cap; contraceptive sponge; condom; vasectomy; or IUD.
    - iii. Use of an IUD with one of the following: condom; diaphragm with spermicide; contraceptive sponge; vasectomy; or hormonal contraception (see above).
    - iv. Vasectomy with one of the following: diaphragm with spermicide; cervical cap; contraceptive sponge; condom; IUD; or hormonal contraception (see above).

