#### 7.5.1 Potential Adverse Events Associated with ORMD-0801

Hypoglycemia and associated symptoms (e.g., weakness, dizziness, shakiness, increased sweating, palpitations, or confusion), have been associated with insulin administration, including ORMD-0801. Animal reproductive studies have not been conducted with ORMD-0801. It is not known whether ORMD-0801 can cause fetal harm when administered to a pregnant woman. It is also not known whether this product is excreted in human milk. Pregnant or breastfeeding women are excluded from this study.

Long-term animal studies have not been completed to assess whether ORMD-0801 impairs fertility.

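### The contraception instruction in Section 3.2 ends about 14 days before the period that inclusion criterion 6a requires, and Section 4.1 contradicts itself on whether women of childbearing potential may enrol

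*Protocol*

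**What the plan says.** **Contraception.** Section 3.2 lists what eligible subjects are told at Screening. The contraception item refers to Section 4.1 for methods and gives its own duration: "for the duration of the study (Screening through Visit 7". Criterion 6a in Section 4.1 sets the duration as "within the projected duration of the trial and for 14 days after the last dose of blinded investigational product". The synopsis version of the criterion has the same tail, "for 14 days after the last dose of blinded investigational product".

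**Population.** Criterion 1 in Section 4.1 limits female subjects to those not of childbearing potential. Criterion 1 in the synopsis has no such limit. In both places, criterion 4 asks women of childbearing potential for a negative serum test, and criterion 6 sets their contraception requirements.

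**Testing.** Section 3.2 lists "Serum pregnancy Test for women of childbearing potential". Section 3.4 (Visit 3) lists "Urine pregnancy Test for women of childbearing potential", and Section 3.6 (Visit 5) does the same. In Table 1 the row "Urine Pregnancy Test" is marked at Visits 3 and 5 only. The Visit 7 sampling line in Section 3.8 reads "Collect fasting blood samples for hematology, serum chemistry (with fasting plasma glucose/FPG), HbA1c and urinalysis" and names no pregnancy test. Section 3.9 (Early Withdrawal) names none either.

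**Risk.** Section 7.5.1 says animal reproductive studies have not been conducted and adds: "It is not known whether ORMD-0801 can cause fetal harm when administered to a pregnant woman". Pregnancy is an exclusion (Section 4.2, item 17) and a reason to end participation (Section 4.3).

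**The concern.** Two places in one protocol give different end points for the same precaution. The shorter one is in the section that tells sites what to say to subjects. Where fetal risk is stated to be unknown, a site should not have to choose between them.

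The contradiction over who may enrol comes first. If criterion 1 of Section 4.1 is read literally, criteria 4 and 6 and the pregnancy tests have no women to apply to. If criteria 4 and 6 are read literally, criterion 1 would turn away women whom the rest of the protocol provides for. Sites could screen the same woman differently and each be following the text. Nothing in the estimation of the treatment effect is at stake. The stakes are subject safety and consistent eligibility across the three sites.

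**Working it through.** The protocol gives no figure of its own to reproduce. The check is a comparison of passages with simple day counts.

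**1. End of the contraception period**

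Inputs: Visit 7 is Day 56 ± 2 (Section 3.8, Table 1). Drug is returned and the subject discharged there (Section 3.8). The tail in criterion 6a is 14 days. Assumption: the last dose is on the day of Visit 7 or the evening before, since Visit 7 is a morning visit and one regimen is taken at bedtime.

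- Under Section 3.2 the period ends at Visit 7: Day 56 (range 54 to 58).
- Under criterion 6a it ends at last dose + 14. With a last dose on Day 56, 56 + 14 = Day 70 (range 54 + 14 = 68 to 58 + 14 = 72). With a last dose on Day 55, 55 + 14 = Day 69.
- Shortfall: 70 − 56 = 14 days, or 69 − 56 = 13 days.

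If dosing stops *d* days before Visit 7, the shortfall is 14 − *d* days and disappears once *d* reaches 14. The figure therefore describes subjects who complete dosing. A subject who withdraws early has no Visit 7, so for her Section 3.2 states no reachable end point and only criterion 6a does.

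**2. Who may enrol**

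- Section 4.1, criterion 1: women of childbearing potential not admitted.
- Synopsis, criterion 1: no such restriction.
- Criterion 4 (both places): presupposes that such women are screened for entry.
- Criterion 6 (both places): presupposes that they take part and are dosed.
- Sections 3.2, 3.4, 3.6 and Table 1: schedule pregnancy tests for them at Screening, Day 1 and Day 28.
- Criterion 5 only defines who is not of childbearing potential and fits either reading.

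One passage points one way and the others the opposite way. The count does not settle which is intended, but they cannot all stand.

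**3. Pregnancy tests (secondary)**

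Inputs: the last scheduled test is at Visit 5, Day 28 ± 2 (Section 3.6, Table 1); study exit is Day 56 ± 2.

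- Nominal gap: 56 − 28 = 28 days.
- Shortest: (56 − 2) − (28 + 2) = 54 − 30 = 24 days.
- Longest: (56 + 2) − (28 − 2) = 58 − 26 = 32 days.
- From the last test to the end of the criterion 6a period: 70 − 28 = 42 days.

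The gap covers the whole second treatment period.

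**The case against.** Section 3.2 cross-refers to Section 4.1, where the 14 days are stated. A subject of childbearing potential cannot enrol without agreeing to them, and the criteria are reviewed at Screening, Visit 2 and Visit 3. Subjects also receive a consent form, which is not among the documents reviewed. This stands in part. A reader might infer that subjects are in fact told to stop at Visit 7; the documents do not show that. But the cross-reference does not remove the conflict, because the sentence containing it names a different end point, and no later visit list corrects it.

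A reader might also infer that the lack of a test at Visit 7 or early withdrawal is an error to be repaired by adding tests there. The documents do not support that. Section 3.8, Section 3.9 and Table 1 agree with one another, and no passage promises an exit test. The on-study urine tests fall at the two visits that start a treatment period, which is a readable logic. No drug is dispensed for use after Visit 7, so a test there could identify a pregnancy for follow-up but could not prevent exposure, and it could not cover the 14 days after the last dose. Unscheduled testing is not forbidden, so it would also go too far to say that a pregnancy in period 2 cannot be found. What remains is that none is scheduled to be looked for, although pregnancy ends participation and fetal risk is unknown.

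Finally, if criterion 1 of Section 4.1 governs, the testing question falls away for female subjects. That is correct, and it is why the population must be settled first.

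**Conclusion.** The point holds as a contradiction within the protocol that bears on safety. The contraception instruction in Section 3.2 is about 14 days shorter than criterion 6a (13 or 14 days for a subject dosed up to Visit 7), and criterion 1 of Section 4.1 conflicts with criteria 4 and 6, the synopsis and the test schedule. The size rests on the last dose falling on or just before Visit 7, and on reading the last dose in criterion 6a as the last dose of randomized ORMD-0801. The criterion calls the product blinded, although the study is open label.

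The 24 to 32 days without a scheduled pregnancy test are a fact of the schedule and a matter for the sponsor to check, not a contradiction. This review takes no view on which contraception period, population or test schedule is right. Sample size and the planned analyses are unaffected.

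**What to change.** 1. Decide which population is intended, and make criteria 1, 4 and 6 of Section 4.1 and the synopsis say the same thing.
2. State one contraception period, with the same start and end, in Section 3.2, Section 4.1 and the synopsis. Make its end clear for a subject who withdraws before Visit 7, and name the product whose last dose is meant.
3. Carry that period into the instructions given to subjects, and check the consent form against it.
4. Check the pregnancy-test schedule against the termination rule in Section 4.3 and the risk statement in Section 7.5.1, and record the reasoning. No particular schedule is proposed here.

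Items 1 to 3 cost a wording amendment with the IRB approval that Section 10 requires, plus any consent form revision that follows. They add no visits or samples. Settling criterion 1 may change who can be recruited; the documents give no figure for how many subjects that would affect.
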